Visits within a subject form a cluster. Estimated proportions by treatment group and visit will be reported. For Week 24 after optimal dose treatment, the log of odds and proportions of subjects who maintain or improve WHO FC and their 95%CI will be reported by treatment groups. Odd ratios (OR) and 95%CI for subjects always on optimal dose (Group 1) relative to those subjects on always on placebo (Group 4) will be reported. OR and 95%CI among subjects always on optimal dose (Group 1) relative to those of subjects on placebo and then active treatment (Group 3) and OR and 95%CI among subjects always on optimal dose (Group 1) relative to those of subjects on non-optimal dose (Group 2) will also be reported.

4) Time to Clinical Worsening

Time to clinical worsening while in the parent trial and LTE will be based on the first occurrence of any of the following events for each subject.

- Death
- Initiation of parenteral prostanoids
- Hospitalization for worsening PAH
- $\geq 15\%$ decline from baseline in 6MWD and accompanied with progression to or continued WHO FC III or IV symptoms

A subject is evaluated for experiencing any of the above components of clinical worsening throughout the parent trial and LTE study period. Time to clinical worsening is the number of days between the earliest occurrence of the clinical worsening component and the date of the first dose in the parent trial. With treatment groups that change over time intervals, event and censoring will be defined within each time interval. A subject who does not experience any of the clinical worsening component throughout a treatment period/interval is censored and is assigned time to worsening status by the end of the interval. Subjects who are lost to follow-up are typically considered censored. Supplemental analyses will be performed where subjects with an unknown clinical worsening event will be considered to

experience the event and the time to clinical worsening status is the last contact with the subject.

The probability of clinical worsening every 24 weeks after the first dose in the parent trial throughout the LTE will be reported, descriptively as well as based on a Cox model for time to clinical worsening while holding covariates at their means.

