dose that a subject achieves clinical improvement in all 3 components from the start through the end of LTE. The number of days between the date that a subject meets all of the multicomponent improvement parameters and the first LTE dose date is the time to achieving multicomponent improvement. A subject who does not experience multicomponent improvement is censored during the time interval. A subject who is lost to follow-up without recording this multicomponent improvement is censored at the last visit in which the above parameters are recorded. Supplemental analyses will be performed where those lost to follow-up are considered a failure at the time of the lost to follow-up.

The Cox hazard model as described for time to clinical worsening will be implemented for time to multicomponent clinical improvement.

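### The supplemental rule for loss to follow-up in time to clinical improvement relies on an undefined failure: read as the Cox event it scores lost subjects as improved, and read as non-response it repeats the main analysis

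*Combined protocol and SAP*

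**What the plan says.** All of this is in Section 8.5.2 of the combined protocol and SAP.

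**Item 5b, time to multicomponent clinical improvement**
- Event time: "The number of days between the date that a subject meets all of the multicomponent improvement parameters and the first LTE dose date". The event is a good outcome.
- Main handling of loss: "A subject who is lost to follow-up without recording this multicomponent improvement is censored at the last visit in which the above parameters are recorded".
- Handling of loss in the supplemental analysis: "Supplemental analyses will be performed where those lost to follow-up are considered a failure at the time of the lost to follow-up".
- Model: "The Cox hazard model as described for time to clinical worsening will be implemented for time to multicomponent clinical improvement".

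**Item 4, time to clinical worsening**
- Main handling of loss: "Subjects who are lost to follow-up are typically considered censored".
- Supplemental handling, in a sentence that runs over a page break: "Supplemental analyses will be performed where subjects with an unknown clinical worsening event will be considered to" and then "experience the event and the time to clinical worsening status is the last contact with the subject".

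The hazard ratios listed in item 4, which item 5b takes over with the model, compare Group 1 with Groups 4, 3 and 2. The plan does not say what failure means in item 5b or how it is coded. Section 8 leaves analysis details to a SAP.

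**The concern.** For clinical worsening, counting a lost subject as an event at last contact assumes the worst, which is what a stress test of censoring should do. Item 5b has a rule of similar form, but there the event is improvement, so counting loss as the event assumes the best. The direction needed to be reversed, and the text does not reverse it.

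This is the only check on loss to follow-up that the plan states for this time-to-event analysis. If it points the wrong way, a difference in attrition can look like a treatment difference, or can hide one. If it repeats the main analysis, agreement between the two will look like robustness that was never tested.

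Balanced loss cannot be taken for granted. Former placebo subjects receive AV-101 for the first time in the extension, whereas Group 1 has already completed 24 weeks on the optimal dose.

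**Working it through.** **Inputs.** The documents give no improvement rate, loss rate, target hazard ratio or power for this analysis, so there is no figure to reproduce. They do give the coding rules quoted above, the two-sided 0.05 level (Section 8.5) and 12-weekly clinic visits after Week 24 (Table 1). Everything else is assumed: constant hazards, improvement hazard λ of 0.30 to 0.45 per year, loss hazard μ of 0.05 to 0.30 per year, 100 subjects per group, two years of follow-up for everyone, improvement read at 12-week visits throughout, and no multiplicity adjustment. Subscripts 1 and 4 denote Group 1 and Group 4.

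**Reading A: failure is the Cox event.** The analysed event is then improvement or loss, whichever comes first, and

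HR = (λ1 + μ1)/(λ4 + μ4).

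- No true effect, loss 0.10 vs 0.05: 0.40/0.35 = 1.14
- No true effect, loss 0.20 vs 0.10: 0.50/0.40 = 1.25
- No true effect, loss 0.30 vs 0.10: 0.60/0.40 = 1.50
- True HR 0.45/0.30 = 1.5, equal loss 0.10: 0.55/0.40 = 1.375
- True HR 1.5, loss 0.05 vs 0.20: 0.50/0.50 = 1.00
- True HR 1.5, loss 0.20 vs 0.05: 0.65/0.35 = 1.857

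**Reading B: failure is non-response dated at the loss.** In a Cox model, a record without an event at its last date is a censored record. The only change from the main analysis is that censoring moves from the last assessed visit to the loss date. On a common visit grid no improvement can be recorded between those dates, so the risk set at every event time is the same. In practice, visit windows leave only trivial differences.

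**Simulation.** Cox model, 400 runs per row. Cells show the hazard ratio, with the share of runs at p<0.05 in brackets. The last column keeps lost subjects as non-improvers to the end of follow-up.

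| True HR | μ1 / μ4 | Main (censored) | Reading A | Reading B | Non-improver to end |
|---|---|---|---|---|---|
| 1.0 | 0.10 / 0.10 | 0.988 (3.7%) | 0.984 (4.3%) | 0.988 (3.7%) | 0.992 (4.0%) |
| 1.0 | 0.20 / 0.10 | 1.015 (4.8%) | 1.266 (24.0%) | 1.015 (4.8%) | 0.913 (5.8%) |
| 1.0 | 0.30 / 0.10 | 1.012 (5.5%) | 1.554 (68.0%) | 1.012 (5.5%) | 0.820 (10.7%) |
| 1.5 | 0.10 / 0.10 | 1.468 (43.2%) | 1.338 (34.7%) | 1.468 (43.2%) | 1.456 (39.3%) |
| 1.5 | 0.05 / 0.20 | 1.521 (48.2%) | 0.969 (5.2%) | 1.521 (48.2%) | 1.781 (76.5%) |
| 1.5 | 0.20 / 0.05 | 1.478 (45.8%) | 1.853 (90.7%) | 1.478 (45.8%) | 1.240 (13.8%) |

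Reading A follows the formula. Reading B equals the main analysis to every digit shown in all six rows. Only the last column moves the estimate against the group that loses more subjects. Across these rows, 13% to 25% of all subjects are lost before improving within two years, so the larger shifts belong to substantial loss.

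**The case against.** **The word is ambiguous.** In item 4 the authors wrote plainly of experiencing the event; in item 5b they wrote of failure, which for an improvement endpoint most naturally means non-response. This stands. A reader might infer that the plan definitely scores lost subjects as improved, and the documents do not settle that. Non-response dated at the loss does not rescue the rule, however, because it is censoring under another name.

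**A third reading is possible.** Failure might mean a non-responder from then on, kept in the risk set, or a competing event. Either would be a sensible analysis. The text supports neither: it dates the failure at the loss and mentions no later risk time and no competing event.

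**The event reading does not always inflate.** This stands. A reader might infer that the rule flatters the always-optimal-dose group. That needs more loss in Group 1. With equal loss a true 1.5 is diluted (1.375 by formula), and with more loss in Group 4 it can vanish (1.00 by formula).

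**The rates are assumed, and loss is narrowly defined.** This stands. Section 6.9 reserves the term for subjects who cannot be reached after repeated attempts, and Section 6.8.1 allows telephone contact after stopping drug. Actual loss may be lower than assumed here, and the shift smaller.

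**Little depends on it.** This also stands. The study objective is long-term safety, the main analysis censors, and item 5a analyses the same endpoint at each visit as a binary response.

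**Conclusion.** The point holds, within limits. As written, the supplemental analysis has two natural readings, and neither gives a check that penalises loss to follow-up. As the Cox event, it shifts the hazard ratio toward the group with more loss and dilutes a true effect when loss is equal. Under the assumed constant hazards with no true effect, the analytic ratio is 1.14 to 1.50 across the unequal-loss cases shown. As non-response at the loss date, it essentially reproduces the main censored result.

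The direction and the equivalence follow from the coding; the sizes rest wholly on assumed rates. A reader might go further and infer that the improvement results, the worsening analysis or the study's conclusions are unsound. The documents do not support that. The main analysis of improvement is unaffected, the worsening rule points the right way for a harmful event, and the safety objective is not involved. The matter is worth correcting because the endpoint is in the first tier and this is its only stated time-to-event check on loss.

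**What to change.** Replace the supplemental sentence in item 5b with: *Supplemental analyses will treat subjects lost to follow-up without improvement as non-improvers, kept in the risk set without an event until their own potential end of follow-up (the data cutoff or study end date, counted from their first LTE dose); loss to follow-up is never coded as the improvement event.*

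The end point must be each subject's own. Entry is staggered from Phase 2b to Phase 3, and Section 3.1 sets a calendar end of 31 December 2025 unless the sponsor stops the study. A single maximum follow-up would credit late entrants with time they could never have had.

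The cost is one sentence in the SAP and one derived date per subject, with no new data. The downside is a deliberate bias against the group with more loss: with no true effect, loss of 0.30 against 0.10 gave 0.82. When Group 4 loses more, the same rule favours Group 1 (1.78 against a true 1.5). It should therefore be labelled a sensitivity analysis that is conservative for the group with more loss, and shown beside the main censored result with the number lost in each group.

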8.5.3 Analysis of Tier 2 Effectiveness Endpoints

- **Change from LTE baseline in echocardiographic parameters at LTE Weeks 24, 48, 72 and 96 including (but not limited to) tricuspid annular peak systolic excursion (TAPSE), right ventricular myocardial strain, tricuspid annular systolic velocity (TA S'), and right ventricular fractional area change (RVFAC):** For each subject, the above echocardiographic parameters will be measured at LTE baseline and Weeks 24, 48, 72, and 96. The mean value and change from baseline at each visit will be summarized descriptively for each treatment group. The mean difference in change from baseline at each visit between subjects always on optimal dose (Group 1) and subjects always on placebo (Group 4) will be summarized and the 95%CI for the difference will be provided. Mean difference and the 95% CI between subjects always on optimal dose (Group 1) and subjects on placebo then active dose (Group 3) will be calculated, followed by taking the difference and the 95% CI between subjects always on optimal dose (Group 1) and subjects on non-optimal dose (Group 2). Mean change from baseline before and after optimal dose treatment during LTE will be presented.
- **Change from baseline in hemodynamics as assessed by RHC in LTE:** For those subjects who have RHC data, change from LTE baseline over time will be summarized for mPAP, PVR, cardiac output and mean right atrial pressure (mRAP), separately, by LTE treatment dose groups. Mean change from baseline before and after optimal dose treatment during the LTE will be presented.

8.6 Safety Analysis

Safety analyses will be conducted using the safety analysis set. The baseline will be defined as prior to the first AV-101 treatment. For Groups 1 and 2, the parent AV-101-002 study baseline will be used. For Groups 3 and 4, the AV-101-003 study baseline will be used and the placebo treatment data from the parent study will not be used. For the analyses of safety parameters, all four groups will be displayed individually. In addition, Groups 1 and 4 will be pooled as the optimal dose treatment group. Groups 2 and 3 will be pooled since they start with the non-optimal dose and then are switched to the optimal dose. An overall pool of all 4 groups will also be presented.

As previously defined, Groups 2 and 3 are treated with the non-optimal dose first and then are converted to the optimal dose. They will be further analyzed based on two treatment intervals. The first interval will start with the first day and end with the last day of the non-optimal AV-101 treatment. The second interval will start with the first day of the optimal AV-101 treatment, and end with the last day of the optimal AV-101 treatment or the data cutoff date for the analysis.

Treatment-emergent AEs (TEAEs), i.e. AEs that start or worsen at the start of AV-101 will be tabulated by system organ class and preferred term. Tables of fatal adverse events, SAEs, treatment-related AEs, and adverse events leading to withdrawal from investigation product will be provided. Subjects who experience more than one event in a given System Organ Class (SOC) and preferred term (PT) will be counted once within that SOC and PT. The total number of events and the number and percentage of subjects with each unique event will be reported.

The latest version of MedDRA will be used to code adverse events and the NCI CTCAE version 5.0 will be used to grade the severity of adverse events and laboratory toxicities.

Tabulations and detailed listings of subjects that experience AEs, AESIs, TEAEs, SAEs and ADEs and unexpected issues with inhaler use will be provided. AE severity and the relationship to AV-101 or the inhaler will also be reported.

For repeated safety events of special interest, incidence density will be compared between treatment arms by fitting a negative binomial model to counts of safety events with total weeks of study participation as an offset variable.

For select safety parameters, descriptive statistics (sample size, mean, standard deviation, median, lower quartile, upper quartile, minimum and maximum) of observed measurements at each visit and of the change from baseline (baseline is defined as the last measurement prior to the first dose of AV-101) to each visit will be presented by visit and by treatment dose groups.

Shift tables for laboratory parameters will be compared among treatment groups by visits. Shift tables may be based on toxicity grading or values classified as low or above normal ranges.

Tabulation and listings of abnormal and/or clinically significant findings/values will be presented for laboratory findings, vital signs, physical examinations, ECG, concomitant medications, concomitant procedures and other safety parameters.

9 Responsibilities

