4.1 Inclusion Criteria

For inclusion in the study, all of the following inclusion criteria must be fulfilled:

1. Subjects who have consented to participate.
2. Subjects who have successfully completed the placebo-controlled 24-week study AV-101-002 without a treatment-limiting toxicity resulting in discontinuation of study drug.
3. Female subjects of childbearing potential who have agreed to continue to use a highly effective form of contraception during the LTE and for at least 30 days after completing or discontinuing study treatment (highly effective forms of contraception are described in [Section 7.8](#)).

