Elective hospitalizations to administer, or to simplify study intervention or procedures are not considered SAEs. However, all events leading to unplanned hospitalizations or unplanned prolongation of an elective hospitalization (i.e., undesirable effects of any administered treatment) must be documented and reported as SAEs.

Events Not to Be Considered as AEs/SAEs

Medical conditions present at the initial study visit that do not worsen in severity or frequency during the study are defined as Baseline Medical Conditions and should be reported in medical history and are not to be considered AEs.

Situations where an untoward medical occurrence has not occurred (e.g., hospitalization for elective surgery, social and/or convenience admissions) are not to be considered as AEs.

7.2 Time Period and Frequency for Collecting Adverse Event and Serious Adverse Event Information

The AE reporting period for safety surveillance begins when the subject is initially included in the study (date of first signature of informed consent/date of first signature of first informed consent) and continues until the last Safety FU per [Table 1](#).

- After informed consent, but prior to initiation of study drug, all SAEs, but only those non-serious AEs related to protocol-mandated procedures should be collected. All AEs that are not related to study procedures should be recorded as worsening medical history.
- Following initiation of study medication, all AEs should be collected, regardless of cause or relationship.
- Events will be summarized on the basis of the date of onset for the event.

A treatment-emergent AE will be defined as any AE that begins on or after the date and time of first dose of study drug through 30 days after last dose of study drug.

Serious Adverse Events

All SAEs, regardless of cause or relationship, that occur after the subject first consents to participate in the study (i.e., signs the informed consent) and throughout the duration of the study, including the protocol-required post treatment follow-up period, must be reported in the eCRF database and to the CRO as instructed. This also includes any SAEs resulting from protocol-associated procedures performed from screening onwards.

Any SAEs and deaths that occur after the post treatment follow-up visit but within 30 days of the last dose of study drug, regardless of causality, should also be reported. Any SAE assessed as

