8.2 Analysis Sets

The following analysis sets will be used to address the specific protocol objectives.

Screened Analysis Set (SAS): The screened analysis set consists of subjects treated at least once in the parent study who signed the informed consent to participate in the LTE study. This is the analysis set for presenting LTE baseline information and the status of subject participation in the LTE study.

Safety (SAF) Analysis Set: The safety analysis set includes all subjects enrolled in the LTE who received at least one dose of treatment during the LTE. This analysis set is the primary analysis set used for all safety summaries.

Full Analysis Set (FAS): The full analysis set includes all subjects enrolled in the LTE who received at least one dose of treatment during the LTE and have at least one post-LTE entry effectiveness measure recorded. This analysis set is the primary analysis set used for all effectiveness analyses.

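### Section 8.6 appears to count Groups 1 and 2 from their first parent-trial AV-101 dose, weeks in which deaths and permanent AE withdrawals cannot appear, and pools them with first-time users

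*Combined protocol and SAP*

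**What the plan says.** Who is analysed: Section 8.2 states "The safety analysis set includes all subjects enrolled in the LTE who received at least one dose of treatment during the LTE". Under Section 4.1, entry requires completing the 24-week parent study "without a treatment-limiting toxicity resulting in discontinuation of study drug".

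From when: Section 8.6 states "For Groups 1 and 2, the parent AV-101-002 study baseline will be used". For Groups 3 and 4 it uses the LTE baseline and adds that "the placebo treatment data from the parent study will not be used". It takes treatment-emergent AEs from the start of AV-101. Groups 2 and 3 are also split at the switch of dose: "The first interval will start with the first day and end with the last day of the non-optimal AV-101 treatment". Section 7.2 defines a treatment-emergent AE as one that "begins on or after the date and time of first dose of study drug", without saying whether the parent or the LTE dose is meant, and it dates events by onset.

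How results are shown: Section 8.6 displays the four groups individually and then states "Groups 1 and 4 will be pooled as the optimal dose treatment group". Groups 2 and 3 are pooled as well, and so are all four groups. Fatal AEs and AEs leading to withdrawal each have their own table. The planned metric is "The total number of events and the number and percentage of subjects with each unique event will be reported".

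Benchmark: comparison 2 of Section 8.1 sets Group 1's LTE safety and effectiveness against the parent period in the same subjects.

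**The concern.** A subject on AV-101 in the parent trial who died, or who stopped the drug for good because of an AE, before Week 24 cannot enter the LTE and so cannot be in the safety set. If Groups 1 and 2 are nevertheless counted from their first parent-trial dose, they bring 24 weeks of AV-101 exposure in which these two outcomes were excluded by selection. Groups 3 and 4 spent those weeks on placebo. Their first 24 weeks on AV-101 fall inside the LTE, where both outcomes can be recorded.

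Long-term safety is the study's primary objective, and the Synopsis says the summaries will support regulatory submissions and DSMB review. A pooled optimal-dose column that mixes 24-week completers with first-time users, or a parent-period benchmark that can only be zero for deaths and AE withdrawals, could be misread on the outcomes that matter most. Other AE types need not be affected in this way, because completers' non-fatal, non-terminating AEs in the parent weeks can be counted.

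**Working it through.** The documents give no AE rates, group sizes or power for the safety analysis, so there is no planned figure to reproduce. All rates below are assumptions.

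**Step 1. Where counting starts.** Four features of Section 8.6 point to the first AV-101 dose in either study:
- the parent baseline for Groups 1 and 2;
- treatment-emergent AEs taken from the start of AV-101;
- Group 2's first interval, which opens on a day that lies in the parent trial;
- the exclusion of parent placebo data only, which would be needless if no parent data were used.

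Two places leave it open: Section 7.2 does not name the study, and the Synopsis's cumulative 24-week intervals have no stated origin.

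**Step 2. Where the two event types can appear.**

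| Group | First AV-101 dose | Death or permanent AE withdrawal possible in AV-101 Weeks 0–24? |
|---|---|---|
| 1 | parent trial | no |
| 2 | parent trial | no (opening part of its first interval) |
| 3 | LTE | yes |
| 4 | LTE | yes |

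For Group 2 subjects who leave the Intermediate Part after dose selection, Section 3.1 assigns the optimal dose at parent Week 24, so their whole first interval lies in the parent weeks. There is one exception to the table. Because events are dated by onset, an AE that began before LTE entry and ended treatment or life afterwards can still be placed in those weeks.

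**Step 3. Effect of the window on the planned percentages.** The denominator is the safety set under either window. Apart from the onset exception, the numerator for these two event types is also the same, because nothing can be added from parent Weeks 0–24. The choice of window therefore leaves the crude percentage unchanged.

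**Step 4. Group 1 against Group 4 over 48 LTE weeks.** Let a be the risk in the first 24 weeks on AV-101 and b the risk in each later 24 weeks. Over these 48 weeks Group 1 is in its second and third such periods, and Group 4 is in its first and second.
- Group 1 = 1 − (1−b)²
- Group 4 = 1 − (1−a)(1−b)
- Group 4 − Group 1 = (1−b)(a−b)

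| Assumed a, b | Group 1 | Group 4 | 1:1 pool | Group 4 − Group 1 |
|---|---|---|---|---|
| 10%, 10% | 1 − 0.9² = 19.0% | 1 − 0.9 × 0.9 = 19.0% | 19.0% | 0 |
| 10%, 3% | 1 − 0.97² = 5.9% | 1 − 0.9 × 0.97 = 12.7% | 9.3% | 0.97 × 0.07 = 6.8 points |
| 3%, 10% | 1 − 0.9² = 19.0% | 1 − 0.97 × 0.9 = 12.7% | 15.85% | 0.9 × (−0.07) = −6.3 points |

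For a from 5% to 20% and b from 1% to 5%, the gap runs from 0 (a = b = 5%) to 0.99 × 0.19 = 18.8 points (a = 20%, b = 1%).

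**Step 5. Comparison 2 of Section 8.1.** If it covers these events, Group 1's parent-period count is zero by construction, onset exception aside. At a constant 10% per 24 weeks, the parent period would show 0% and the first 24 LTE weeks 10%, with no change in risk.

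**Step 6. Against everyone who started AV-101.** Let q be the crude percentage among LTE entrants, d the share of AV-101 starters who died or withdrew for an AE before Week 24, and m the share who did not enter the LTE for any reason. Counting observed events, all starters show d + (1−m)q. This exceeds q only if d/m > q. The documents give none of the three quantities.

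**The case against.** The strongest reply is that an extension study enrols completers and this one says so. The planned metric is a crude percentage, which Step 3 shows is the same under either window. Section 8.1 presents LTE safety by LTE visit intervals, and the parent baseline in Section 8.6 may serve only change-from-baseline summaries. The four groups are shown separately and Groups 2 and 3 are split by interval. Groups 3 and 4 also survived 24 parent weeks, so for deaths driven by the disease all groups are selected in a similar way. Section 8 leaves further detail to an SAP.

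Much of this stands. It rules out several stronger conclusions that a reader might draw:
- *Group 1 will look safer than Group 4 by design.* For crude percentages this needs risk to fall with time on drug, which the documents do not show.
- *Rates are diluted by 24 event-free weeks.* Under a constant hazard, a person-time analysis could indeed show a true rate ratio of 1.00 as about 0.65 at 48 LTE weeks. But Section 8.6 plans incidence density only for repeated events of special interest, not for death or permanent withdrawal.
- *The tables understate risk relative to all AV-101 starters.* Step 6 shows that the direction for the crude percentage is not established.
- *The 92 subjects between 462 and 370 are attrition.* The protocol gives 462 as the maximum LTE size and never as the number treated in the parent study.

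The reply leaves three things unanswered. Separate display does not remove the built-in zero from Group 1's parent weeks or from Group 2's first interval. Comparison 2 still uses selected parent time as its benchmark. The pools still combine completers with first-time users, even if Groups 1 and 2 are counted from LTE Day 1.

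**Conclusion.** The point holds in a limited form and is worth fixing. That deaths and permanent AE withdrawals are missing from the parent AV-101 weeks of Groups 1 and 2 follows directly from Sections 4.1 and 8.2. That Section 8.6 counts those weeks is the best reading of its wording, but it is nowhere stated outright. The consequence is confined to these two event types and to three places: Group 2's first interval, the Group 1 benchmark in comparison 2, and the interpretation of the 1+4, 2+3 and overall pools.

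The size depends on risks that the documents do not give. Under the assumed 10% then 3%, Group 1 shows 5.9%, Group 4 shows 12.7%, and a 1:1 pool shows 9.3%, which describes neither group. At constant risk there is no difference between Groups 1 and 4, and with rising risk the sign changes. No general claim that the crude tables understate risk is supported.

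**What to change.** In Section 8.6, or in the SAP with a cross-reference:
1. State the AE counting window for each group and the origin of the 24-week intervals. Say how an AE with onset before LTE entry that leads to death or withdrawal afterwards is dated.
2. Tabulate fatal AEs and AEs leading to withdrawal by interval since first AV-101 dose, with the number at risk in each interval. For these events, count Groups 1 and 2 as at risk only from LTE Day 1, and label them as 24-week completers.
3. Do not use the parent weeks of Groups 1 and 2 as event-free time in the 1+4, 2+3 or overall pools.
4. For these events in comparison 2 of Section 8.1, take the Week 0–24 benchmark from all AV-101-treated parent subjects in the matching arm, or cross-refer to the AV-101-002 results. Do not use LTE entrants only.

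The cost is some wording and a few extra tables. Item 4 draws on AV-101-002 data beyond the LTE safety set; the cross-reference option avoids a cross-study analysis. The early-event figures are likely to be less favourable than those from LTE entrants alone.
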